### **Contraception**

From signing of the informed consent through the duration of the study (and for no less than 30 days after last dose of study medication), female subjects of childbearing potential\* who are sexually active with a nonsterilized male partner\*\* must use adequate contraception. In addition they must be advised not to donate ova during this period.

\*Females NOT of childbearing potential are defined as those who have been surgically sterilized (hysterectomy, bilateral oophorectomy or tubal ligation) or who are postmenopausal (e.g., defined as at least 1 year since last regular menses with an FSH>40 IU/L or at least 5 years since last regular menses, confirmed before any study medication is implemented).

**\*\*Sterilized males should be at least 1 year post-vasectomy and have confirmed that they have obtained documentation of the absence of sperm in the ejaculate.**

An acceptable method of contraception is defined as one that has no higher than a 1% failure rate.

In this study, the only acceptable methods of contraception are:

- Barrier methods (male condom PLUS spermicide; cap (plus spermicidal cream or jelly) PLUS male condom and spermicide; diaphragm (plus spermicidal cream or jelly) PLUS male condom and spermicide
- Intrauterine devices (IUDs) (copper T PLUS condom or spermicide; progesterone T PLUS condom or spermicide
- Hormonal contraceptives (implants; hormone shot/injection; combined pill; minipill; patch; vaginal ring PLUS male condom and spermicide)

Female subjects will be provided with information on acceptable methods of contraception as part of the subject informed consent process and will be asked to sign a consent form stating that they understand the requirements for avoidance of pregnancy and donation of ova during the course of the study and within 30 days following the study completion.

A urine pregnancy test will be performed at the screening visit for women of childbearing potential and may be repeated at the investigator's discretion.

### **Pregnancy**

If any subject is found to be pregnant or breastfeeding during the study, she will be withdrawn and any sponsor-supplied drug will be immediately discontinued.

If the pregnancy occurs during administration of active study medication (e.g., after Visit 2 or within 30 days of the last dose of active study medication), the pregnancy will be reported immediately to the IRB using standard procedures per the sponsor and PI.

If the female subject agrees to her primary care physician being informed, the investigator will notify the primary care physician that the subject was participating in a clinical study at the time she became pregnant and provide adequate details of treatment the subject received.

All pregnancies discovered post-baseline will be referred to the subject's primary care physician, obstetrician or other designated medical care provider and followed via regular communication for 30 days (including any premature termination).

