### Duration of Vortioxetine Treatment:

One dose daily for 8 weeks.

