**Other Risks**

Whenever a subject is determined to be at risk for suicide during a clinical visit by the examining clinician, she or he will be escorted to the nearest emergency room.

We will not share information about subjects' participation in this study with others to minimize risks relative to subjects' privacy. Every effort will be made to keep participation confidential. These issues will be clearly stated in consent forms and discussed with participants during the informed consent procedure.

Consistent with good clinical practice, safety will be monitored by each subject's assigned clinician at each study visit. This clinician will be available 24 hours a day by page. The PI will supervise all study activities including ratings, reported adverse events, laboratory tests, and vital signs. Subjects will be monitored for adverse events at each visit and during phone communications with the clinician. All adverse events will be recorded.

All procedures will aim to minimize subject discomfort, and no subject will be asked to engage in research procedures not outlined in the consent form. All adverse events will be reported to the PHRC according to PHRC guidelines.

Subjects who are judged to experience a worsening of depressive symptoms as manifested by a CGI-Improvement rating of 6 or more (1=Very much improved, 2=Much improved, 3=Minimally improved, 4=No change, 5=Minimally worse, 6=Much worse, 7=Very much worse) or per the investigator's opinion for 2 consecutive visits the subject may be removed from the study and provided referrals as appropriate.

Subjects with MDD will be offered three months of follow-up care at the completion of the study (or if they are required to discontinue for any reason) in which they will be seen by study staff for routine outpatient management of their MDD. Subjects will receive referrals to clinicians in their communities, either at the end of the 3 month period, or sooner upon their request or circumstances require such a referral as determined by the investigator.

If a subject becomes pregnant or is found to be abusing substances during the study, he or she will be discontinued from the study and given referrals.

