#### **MONITORING/REPORTING OF AE/SAE COLLECTION AND RECORDING:**

*Adverse event* means any untoward medical occurrence associated with the use of a drug in humans, whether or not considered drug related.

*Life-threatening adverse event or life-threatening suspected adverse reaction.* An adverse event or suspected adverse reaction is considered "life-threatening" if, in the view of either the investigator or sponsor, its occurrence places the patient or subject at immediate risk of death. It does not include an adverse event or suspected adverse reaction that, had it occurred in a more severe form, might have caused death.

*Serious adverse event or serious suspected adverse reaction.* An adverse event or suspected adverse reaction is considered "serious" if, in the view of either the investigator or sponsor, it results in any of the following outcomes: Death, a life-threatening adverse event, inpatient hospitalization or prolongation of existing hospitalization, a persistent or significant incapacity or substantial disruption of the ability to conduct normal life functions, or a congenital anomaly/birth defect. Important medical events that may not result in death, be life-threatening, or require hospitalization may be considered

serious when, based upon appropriate medical judgment, they may jeopardize the patient or subject and may require medical or surgical intervention to prevent one of the outcomes listed in this definition. *Suspected adverse reaction* means any adverse event for which there is a reasonable possibility that the drug caused the adverse event. For the purposes of IND safety reporting, “reasonable possibility” means there is evidence to suggest a causal relationship between the drug and the adverse event. Suspected adverse reaction implies a lesser degree of certainty about causality than adverse reaction, which means any adverse event caused by a drug.

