**APPENDIX I - SCHEDULE OF EVENTS**

Visit #	Screen 1	Baseline 2	3	4	5	6	7	8	9	10 (or ET)
Day	-2 to -14	0	7	14	21	28	35	42	49	56
Week	-1 to-2	0	1	2	3	4	5	6	7	8
Informed Consent	X									
Incl/Excl Criteria	X	X								
MINI	X									
ASRS	X									
Medical and Psychiatric History	X									
Demographics	X									
Physical Exam	X									
Laboratory tests, urinalysis, urine pregnancy test and urine drug screen 	X									
Vital signs and weight 	X	X	X	X	X	X	X	X	X	X
Height		X								
12-Lead ECG	X									
HDRS (28-item)	X	X	X	X	X	X	X	X	X	X
QIDS-SR-16	X	X	X	X	X	X	X	X	X	X
MADRS	X	X	X	X	X	X	X	X	X	X
DSST	X									X
UPSA	X									X
TMT-A AND TMT-B	X									X
Stroop Test	X									X
MGH-CPFQ	X	X	X	X	X	X	X	X	X	X
PDQ	X	X	X	X	X	X	X	X	X	X
CGI-S	X	X	X	X	X	X	X	X	X	X
CGI-I			X	X	X	X	X	X	X	X
WLQ	X	X	X	X	X	X	X	X	X	X
C-SSRS 	X	X	X	X	X	X	X	X	X	X
Concomitant therapy	X	X	X	X	X	X	X	X	X	X
Study drug dispensed		X	X	X	X	X	X	X	X	
Study drug accountability			X	X	X	X	X	X	X	X
Adverse events	X	X	X	X	X	X	X	X	X	X
EEG (BNA reading)	X	X		X						X

may be repeated at investigator's discretion

including body temperature (oral), blood pressure and pulse.

C-SSRS lifetime version at screen only; Since Last Visit version at V2-10

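### Pregnancy follow-up stops after 30 days, with no start point given, and no contact is scheduled in the 30-day post-dose reporting window, so birth outcomes are not systematically captured

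*Combined protocol and SAP*

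**What the plan says.** All references are to the combined protocol and SAP.

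- **Pregnancy:** a pregnant subject is withdrawn and study drug is stopped. Any pregnancy found after baseline is referred to the subject's own care provider and "followed via regular communication for 30 days (including any premature termination". The section does not say when the 30 days begin. Immediate reporting to the IRB applies to pregnancies occurring "after Visit 2 or within 30 days of the last dose of active study medication".
- **Contraception:** required throughout the study and "for no less than 30 days after last dose of study medication". On testing: "A urine pregnancy test will be performed at the screening visit for women of childbearing potential and may be repeated at the investigator's discretion".
- **Monitoring/Reporting of AE/SAE:** the outcomes that make an event serious include "a persistent or significant incapacity or substantial disruption of the ability to conduct normal life functions, or a congenital anomaly/birth defect". The same section says that pregnancy is not in itself an adverse experience and leaves its notification to IRB requirements and the investigator's practice. Adverse events still ongoing when a subject finishes are followed until they resolve, stabilise or are otherwise explained.
- **Appendix I, Schedule of Events:** the adverse-event row reads "Adverse events X X X X X X X X X X", and the last column is Visit 10 or early termination (Day 56 for completers).
- **Other Risks:** "Subjects with MDD will be offered three months of follow-up care at the completion of the study", or on discontinuation for any reason. Study staff give this care as ordinary outpatient treatment of depression.

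**The concern.** The pregnancy rule and the seriousness definition do not fit together. A birth defect becomes known at or near birth in most of the cases that matter here, and a site that applies the 30-day rule from discovery will have closed the case months before. The safety data could then hold an exposed pregnancy with no known outcome.

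Detection is a second, smaller problem. The plan asks subjects to avoid pregnancy, and asks the site to report it, for 30 days after the last dose, but plans no occasion in that period on which anyone asks. At stake are the safety of a subject and her infant and the completeness of safety reporting. The efficacy and BNA results are not involved.

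**Working it through.** The plan gives no figure to reproduce. The check is day arithmetic on the schedule.

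**Inputs from the document**
- Treatment: "One dose daily for 8 weeks", so the last dose is at about Day 56 (Day 55 on a strict count).
- Pregnancy reporting and contraception window: 30 days after the last dose.
- Pregnancy follow-up: 30 days, start not defined.
- Offered post-study care: three months, taken as 84 to 92 days.
- Screening: up to 14 days before the first dose. It carries the only required pregnancy test.
- Subjects: 40. Contraceptive failure: no higher than 1%.

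**Assumptions not in the document**
- Conception to birth: 266 days (range 252 to 280).
- Discovery: 14 to 42 days after conception.
- The 1% failure figure is annual.

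**1. Does follow-up reach birth?** Start the clock at discovery, the natural reading. The gap between end of follow-up and birth is (conception to birth) − (conception to discovery) − 30.
- Discovery at 14 days: 266 − 14 − 30 = 222 days short.
- Discovery at 42 days: 266 − 42 − 30 = 194 days short.
- Extremes of the ranges: 252 − 42 − 30 = 180 and 280 − 14 − 30 = 236 days short.

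Conception may also precede the first dose, because the follow-up rule covers every pregnancy discovered after baseline. Take conception at Day −28 and discovery as late as Day 86. Follow-up ends at Day 86 + 30 = 116, birth falls at −28 + 266 = Day 238, and the gap is 238 − 116 = 122 days.

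If the clock started at pregnancy outcome the gap would vanish, but nothing in the text says so.

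**2. Does the offered care reach birth?** For a completer it ends between Day 56 + 84 = 140 and Day 56 + 92 = 148. The earliest term birth for conception on or after Day 0 is Day 252, so the care ends at least 252 − 148 = 104 days before it.

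**3. Does the adverse-event follow-up rule help?** It keeps ongoing adverse events open. Since the protocol says pregnancy is not one, an uncomplicated pregnancy is not kept open by it.

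**4. Is the post-dose window covered?** It runs from Day 56 to Day 56 + 30 = 86 for completers. Appendix I has no visit, call or pregnancy test in it. An early terminator likewise has nothing scheduled in the 30 days after stopping. The offered care outlasts the window by 140 − 86 = 54 to 148 − 86 = 62 days for completers who accept it, but has no pregnancy enquiry attached.

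**5. How many pregnancies?** Upper bound, treating all 40 subjects as at risk over 86 days: 40 × (86/365) × 0.01 = 0.09.

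**The case against.** A reader might infer that the plan makes these events impossible to observe. It does not. The 30-day follow-up expressly takes in premature termination, so an anomaly found at an early loss could be recorded. A pregnancy may be self-reported, and the protocol then requires immediate IRB notification. The safety-reporting section covers serious risks from any source, so an outcome learned of later is not barred. The offered care puts willing subjects in touch with study staff throughout the 30-day window. All of this stands. What is missing is a planned step that asks the question.

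A reader might also infer that the safety conclusion rests on too short a collection period, or that suicidal behaviour after stopping is left out contrary to the plan. The documents do not support that. The 30-day window governs contraception and pregnancy reporting only. No section sets a post-dose window for serious adverse events, and the stated safety outcome concerns the 8 weeks of treatment.

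It is fair, too, that a list of seriousness criteria classifies events once known and does not promise active ascertainment, so this is not a strict contradiction. The protocol also defers to sponsor, investigator and IRB procedures, and the consent pages are not available here; either may tell subjects to report a pregnancy. That limits how firmly one can speak about self-report. It does not alter the 30-day limit written in the protocol, which is what a site will follow.

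**Conclusion.** The point holds as a gap in planned ascertainment. With the clock starting at discovery, follow-up ends about 194 to 222 days before a term birth under the central assumptions, 180 to 236 days over the ranges shown, and still 122 days before in the unfavourable case of conception before dosing and late discovery. The gestation and discovery intervals are assumptions, but the conclusion does not turn on their exact values. It does rest on the clock not starting at pregnancy outcome, and the missing start point is itself worth correcting. No scheduled contact falls in the 30 days after the last dose.

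It would be wrong to go further and say that the events can never be recorded, or that conception must follow the first dose. With at most about 0.09 pregnancies expected, the practical yield is small and no efficacy or BNA analysis changes. This is a cheap improvement to subject safety and to the working of the protocol's own reporting rules.

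**What to change.** - In the Pregnancy section, replace the 30-day limit with follow-up to pregnancy outcome, including newborn status, by telephone and with the subject's consent. This also removes the undefined start point.
- Add to Appendix I one telephone contact 30 days after the last dose, for completers and early terminators alike, that asks about pregnancy. The same call can record new serious adverse events. Where a subject has accepted the three-month care, the enquiry can be made there.
- Reconcile the Contraception, Pregnancy, Other Risks and AE/SAE sections and Appendix I so that they describe one consistent procedure.

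Cost: one call per subject, a place to record the answer, and an amendment to protocol and consent form that needs IRB approval, including consent for newborn information. A rare pregnancy would keep one case file open for months after the trial. No dose, treatment or withdrawal rule is touched.

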### **STUDY PROCEDURES**

See Schedule of Events (Appendix I) for complete list of study procedures performed at each visit.

All BNA procedures will be done as early in the visit as possible to avoid any confounding factors that may impact the outcome, except during the screen visit (at this visit, the BNA will occur after the subject completes the informed consent process and clinician-assessed inclusion/exclusion criteria are assessed). The screening visit can be split into 2 visits, as long as the screening period does not exceed the 14-day screen period.

### **Visit 1 (Screen)**

- Following the informed consent process, subjects will begin the Screening Visit (Visit 1), which will include a psychiatric/medical history, vital signs, urinalysis, urine drug screen, urine pregnancy test (females), EEG/BNA, blood drawn for laboratory tests (CMP, CBC w/diff, TSH), ECG, and clinician- and patient-rated scales.

### **Visits 2-10**

#### All Subjects

- Subjects who meet all inclusion criteria and no exclusion criteria following the screening visit will enter the study. Weekly study visits will be conducted for efficacy, safety, and tolerability. No dose changes will be allowed after Visit 8.
- A baseline EEG/BNA will be taken before the subject begins taking vortioxetine and follow-up EEG/BNA readings will be taken at Visit 4, and Visit 10 (or last study visit if a subject is withdrawn early).
- Vital signs, review of adverse events, study drug accountability and clinician- and patient-rated scales will be conducted at specific study visits.

### **Description of BNA**

BNA is a method of analyzing electrophysiological and neuropsychological brain network activity using multichannel signals acquired by EEG/ERP non-invasive system hardware. The following sections describe the EEG methodology and the neurocognitive tasks.

### **EEG Procedures**

Subjects will be fitted with a net containing 64 EEG electrodes. While wearing the net, subjects will complete a series of cognitive tasks during which time data will be collected.

Standard EEG recording will be performed using the FDA system manufactured by Electrical Geodesics, Inc (EGI) from 64 locations by using Ag-AgCl electrodes mounted in an elastic net, referenced to electrode Cz. Channels will be sampled at 250 Hz.

The EEG system complies with the standard electrical safety (EN 60601-1) and EMC compatibility. During the recording of ERPs, triggers sent by the test presentation script to mark the onset of the stimuli and the subject response are recorded concurrently with EEG signals.

### **Neurocognitive tests (ERPs)**

The following battery of tasks will be performed by subjects during the EEG. If total recording time reaches 60 minutes, the Delayed match-to-sample task below may be excluded.

**Eyes Open/Eyes Closed tasks:** EEG will be recorded at rest (no cognitive task), 2 minutes with eyes open and 2 minutes with eyes closed. The aim of the resting EEG recording is to extract patterns of the default mode network (DMN). The DMN is a network comprising many brain regions which show in fMRI studies reduced activation during task execution. Recently, the DMN has been studied also in EEG signals (Laufs et al. 2003). There is evidence that the DMN is impaired during emotional processing in MDD patients (for example see Grimm et al. 2009).

**Auditory oddball task:** The oddball task is a classic EEG paradigm that has been extensively used for many years, in numerous studies and in many neurological patient populations. It is considered to

involve executive functions, attention and memory processes. During the task, sounds will be presented, at an average rate of 1 every 1.5 sec. A total of 80% of the sounds ("standard") will be tones of repeating frequency and intensity. A total of 10% of the sounds ("target") will be tones of another frequency to which participants will respond by pressing a button. The remaining 10% of sounds ("novel") will be multi-frequency sounds, different for each trial). Segments of 1200 ms will be averaged separately for "standard", "target," and "novel" sounds. The task duration is approximately 12 minutes.

**Visual Go-NoGo:** The Go stimuli consist of white color English alphabetic letters the NoGo stimuli consist of white colored X symbol. The NoGo appears 20% of the time and the Go stimuli appears 80%. The stimuli are presented in the center of a black background computer screen for 150 ms, and are located between two vertical white lines which remain constant on the screen. Subjects are instructed to press a key as quickly as they can when presented with the Go stimulus and withhold pressing the key when the NoGo stimulus appears. The task duration is approximately 14 minutes.

**Delayed match-to-sample:** Memory and emotional processing related evoked potentials will be measured by presenting pairs of fearful or neutral faces with a delay of 1.8 sec. Subjects will judge whether the second face stimulus matches or not the first one. The task duration is approximately 13 minutes.

**Optional tasks:**

If recording time allows, additional, optional tasks may be completed which will be chosen from the following list, for a total EEG recording time of approximately 45-60 minutes.

**Inter hemispheric transfer time (IHTT):** In this task the subject needs to count red dots that appear in the middle of the screen while white squares flashes either in the left or right visual fields. At the end of each block the subject reports the number of red dots. The inter-hemispheric transfer time is calculated from the evoked response to the peripheral stimuli. The task duration is approximately 12 minutes.

**Auditory Go/No Go test:** The Go/NoGo paradigm is among the most well-characterized assays of response inhibition to perceptual stimuli. Go/NoGo tasks involve the presentation of a continuous series of "Go" or "target" cues to which subjects are asked to respond as quickly as possible, and "NoGo" or "distractor" cues that require subjects to inhibit motor responses. ERP studies reliably identify a negative-going component occurring 200 – 400 ms following NoGo stimuli known as the "NoGo N2", which occurs maximally at fronto-central scalp locations. On NoGo trials, the N2 is followed by a positive-going shift. This positive complex, termed the "NoGo P3", also occurs maximally at fronto-central scalp sites and is typically seen 300 – 700 ms following the NoGo stimulus. There is evidence showing a specific deficit in response inhibition in depressed patients, which requires executive control.

Both ERP source localization and fMRI data have demonstrated that the right ventral lateral prefrontal cortex (PFC), particularly the inferior frontal gyrus (IFG), is consistently activated with successful motor control on Go/NoGo tasks, and lesions to the IFG impair such inhibitory control. The IFG has been showing abnormal activity and connectivity in MDD. Based on these observations, the Go/NoGo may be a useful tool for assessing well-defined neural pathways in major depression. The task duration is approximately 18 minutes.

**LDAEP:** Subjects are seated with open eyes and are asked to look at a fixation cross in front of them. Tones (1000 Hz, 40 ms duration with 10 ms rise and 10 ms fall time, ISI randomized between 1800 and

2200 ms) of five intensities (54, 64, 74, 84, 94 dB sound pressure level) are presented binaurally in a pseudorandomized form by earphones. Before the study, the sound pressure level of the headphones should be calibrated with a sound level. The task duration is approximately 13 minutes.

